**8.4.4.4. Cardiovascular Events**

Investigators will be required to fill out event specific data collection tools for the following AEs and SAEs:

- Myocardial infarction/unstable angina
- Congestive heart failure
- Arrhythmias
- Valvulopathy
- Pulmonary hypertension
- Cerebrovascular events/stroke and transient ischemic attack

- Peripheral arterial thrombosis
- Deep Venous Thrombosis
- Revascularization

This information should be recorded within one week of when the AE/SAE(s) are first reported.

#### **8.4.4.5. Death Events**

In addition, all deaths, whether or not they are considered SAEs, will require a specific death data collection tool to be completed. The death data collection tool includes questions regarding cardiovascular (CV) (including sudden cardiac death) and noncardiovascular death.

This information should be recorded within one week of when the death is first reported.

#### **8.4.4.6. Disease-Related Events and/or Disease-Related Outcomes Not Qualifying as SAEs**

##### **8.4.4.6.1. Cohort A (MDS/AML Adult Subjects)**

An event which is part of the natural course of the disease under study (i.e., infections, cachexia, anorexia, disease progression or hospitalization due to disease progression) should not be reported as an AE or SAE. If the clinical course is worse than that which would normally be expected for the subject, or if the investigator considers that there was a causal relationship between treatment with study medication(s) or protocol design/procedures to the course of the underlying disease, then this must be reported as an SAE. Furthermore, death due to disease under study is to be recorded on the Death CRF form and the specific cause of death must be recorded (e.g. sepsis, gastrointestinal hemorrhage, etc), rather than 'disease under study' or 'progressive disease'.

##### **8.4.4.6.2. Cohort B and Cohort C (ITP Adult and Pediatric Subjects)**

During the assessment period, thrombocytopenia that results in the administration of rescue medication is to be considered treatment failure rather than AEs or SAEs. Also during this assessment period, hospital admissions that are attributable to such treatment failures or related therapy also do not qualify as AEs or SAEs. Hemorrhagic complications of thrombocytopenia not otherwise meeting regulatory serious criteria (see Section 8.4.4.2. Definition of a SAE) will be reported as AEs.

#### **8.4.5. Time Period and Frequency of Detecting AEs and SAEs**

The investigator or site staff is responsible for detecting, documenting and reporting events that meet the definition of an AE or SAE.

AEs will be collected from the time of ICF signature until 30 days following discontinuation of study treatment regardless of initiation of a new cancer therapy or transfer to hospice.

SAEs will be collected over the same time period as stated above for AEs. In addition, any SAE assessed **as related** to study participation (e.g., protocol-mandated procedures, invasive tests, or change in existing therapy), will be reported promptly to Novartis within 24 hours, as indicated in Section 8.4.7.

After discontinuation of study treatment, the investigator will monitor all AEs/SAEs that are ongoing until resolution or stabilization of the event or until the subject is lost to follow-up. At any time after 30 days the investigator may report any adverse event that they believe possibly related to study treatment.

#### **8.4.6. Method of Detecting AEs and SAEs**

Care must be taken not to introduce bias when detecting AEs and/or SAEs. Open-ended and non-leading verbal questioning of the subject is the preferred method to inquire about AE occurrence. Appropriate questions include:

“How are you feeling?” or for pediatric studies, “How does your child seem to feel?”

“Have you had any (other) medical problems since your last visit/contact?” or for pediatric studies, “Has your child had any (other) medical problems or seem to act differently in any way since his/her last visit/contact?”

“Have you taken any new medicines, other than those provided in this study, since your last visit/contact?” or for pediatric studies, “Has your child needed to take any medicines, other than those provided in this study, since his/her last visit/contact?”

#### **8.4.7. Prompt Reporting of SAEs and Other Events to Novartis**

SAEs, pregnancies, and liver function abnormalities meeting pre-defined criteria will be reported promptly by the investigator to Novartis as described in the following table once the investigator determines the event meets the protocol definition for that event.

Type of Event	Initial Reports		Follow-up Information on a Previous Report	
	Time Frame	Documents	Time Frame	Documents
All SAEs	24 hours	SAE data collection tool “CV events” and/or “death” data collection tool(s) if applicable	24 hours	Updated SAE data collection tool “CV events” and/or “death” data collection tool(s) if applicable
Pregnancy	24 hours	Pregnancy Notification Form	2 Weeks	Pregnancy Follow up Form
Liver chemistry abnormalities:				
ALT $\geq$ 3xULN and bilirubin $\geq$ 2xULN (>35% direct) (or ALT $\geq$ 3xULN and INR>1.5, if INR measured) c	24 hours a	SAE data collection tool. Liver Event Case Report Form (CRF) and liver imaging and/or biopsy CRFs if applicable b	24 hours	Updated SAE data collection tool. Updated Liver Event CRF b
ALT $\geq$ 5xULN; ALT $\geq$ 3xULN with hepatitis or rash or 3xULN $\geq$ 4 weeks	24 hours a	Liver Event CRF b	24 hours	Updated Liver Event CRF b
ALT $\geq$ 3xULN and <5xULN and bilirubin <2xULN	24 hours a	Liver Event CRF does not need completing unless elevations persist for 4 weeks or subject cannot be monitored weekly for 4 weeks b		
a) Novartis to be notified at onset of liver chemistry elevations to discuss subject safety. b) Liver Event Documents (i.e., “Liver Event CRF” and “Liver Imaging CRF” and/or “Liver Biopsy CRF”, as applicable) should be completed as soon as possible c) INR measurement is not required; if measured, the threshold value stated will not apply to subjects receiving anticoagulants.				

Methods for recording, evaluating, and following up on AEs and SAES and procedures for completing and transmitting SAE reports to Novartis are provided in the SPM. Procedures for post-study AEs/SAEs are provided in the SPM.

Prompt notification of SAEs by the investigator to Novartis is essential so that legal obligations and ethical responsibilities towards the safety of subjects are met.

Novartis has a legal responsibility to notify both the local regulatory authority and other regulatory agencies about the safety of a product under clinical investigation. Novartis will comply with country specific regulatory requirements relating to safety reporting to the regulatory authority, Institutional Review Board (IRB)/Independent Ethics Committee (IEC) and investigators.

Investigator safety reports are prepared for suspected unexpected serious adverse reactions according to local regulatory requirements and Novartis policy and are forwarded to investigators as necessary.

An investigator who receives an investigator safety report describing a SAE(s) or other specific safety information (e.g., summary or listing of SAEs) from Novartis will file it with the IB and will notify the IRB/IEC, if appropriate according to local requirements.

#### **8.4.8. Pregnancy, Testing, Prevention and Reporting**

Clear documentation of post-menopausal status (as defined in Section 8.4.8.1.) must be included in each subject's source documents as applicable. Female subjects with this documentation of post-menopausal status are considered to be of non-childbearing potential and do not need to have pregnancy tests performed during this trial. Female subjects without documentation of post-menopausal status are considered to be of childbearing potential and will be required to undergo pregnancy testing at the Transition Visit and prior to first study treatment.

In the event that a pregnancy does occur, the subject will be immediately withdrawn from the study. The subject will receive counselling from the investigator or his/her designee, regarding the nature of the study treatment and the potential risk on fetal development.

##### **8.4.8.1. Pregnancy Testing and Prevention**

The need for a screening pregnancy test depends on whether a female subject is of childbearing potential or non-childbearing potential.

**A female of non-childbearing potential** (i.e., physiologically incapable of becoming pregnant) is defined as any female who is pre menarchal, or who has had a hysterectomy, bilateral oophorectomy (ovariectomy) or bilateral tubal ligation, or is post-menopausal.

A practical definition accepts menopause after 1 year without menses with an appropriate clinical profile, e.g., age appropriate, >45 years in the absence of hormone replacement therapy (HRT). In questionable cases, the subject must have a follicle stimulating hormone (FSH) value >40 mIU/mL and an estradiol value < 40pg/mL (<140 pmol/L). Postmenopausal status must be documented in the subject's source documentation.

**A female of child-bearing potential** is defined as any female who does not meet the criteria of non-childbearing potential as described in the previous paragraph.

If a female subject is of childbearing potential, she must have a serum  $\beta$ -HCG pregnancy test performed within 14 days prior to the first dose of study treatment. Subjects with a positive pregnancy test result must be excluded from the study. Subjects with a negative

pregnancy test result must agree to use an effective contraception method as described below during the study until 28 days following the last dose of study treatment.

Novartis acceptable contraceptive methods, when used consistently and in accordance with both the product label and the instructions of the physician, are as follow:

- An intrauterine device with a documented failure rate of less than 1% per year.
- Vasectomized partner who is sterile prior to the female subject's entry and is the sole sexual partner for that female.
- Complete abstinence from sexual intercourse for 14 days prior to first dose of study treatment, through the dosing period, and for at 28 days after the last dose of study treatment.
- Double-barrier contraception: condom and occlusive cap (diaphragm or cervical/vault caps) with a vaginal spermicidal agent (foam/gel/cream/suppository).
- Implants of levonorgestrel where not contraindicated for this patient population or per local practice.
- Injectable progesterone where not contraindicated for this patient population or per local practice.
- Oral contraceptives (either combined or progesterone only) where not contraindicated for this patient population or per local practice.

Female subjects who are lactating must discontinue nursing prior to the first dose of study treatment and must refrain from nursing throughout the treatment period and 28 days following the last dose of study treatment.

#### **8.4.8.2. Pregnancy Reporting**

Any pregnancy that occurs during study participation must be reported using a clinical trial pregnancy form. To ensure subject safety, each pregnancy must be reported to Novartis within 24 hours of learning of its occurrence. The pregnancy must be followed up to determine outcome (including premature termination) and status of mother and child. Pregnancy complications and elective terminations for medical reasons must be reported as an AE or SAE. Spontaneous abortions must be reported as an SAE.

Any SAE occurring in association with a pregnancy brought to the investigator's attention after the subject has completed the study and considered by the investigator as possibly related to the study treatment, must be promptly reported to Novartis.

In addition, the investigator must attempt to collect pregnancy information on any female partners of male study subjects who become pregnant while the subject is enrolled in the study. Pregnancy information must be reported to Novartis as described above.

## **9. DATA MANAGEMENT**

For this study, subject data will be entered into the electronic case report forms (eCRFs), transmitted electronically to Novartis or designee and be combined with data provided from other sources in a validated data system.

Management of clinical data will be performed in accordance with applicable Novartis standards and data cleaning procedures to ensure the integrity of the data, e.g., resolving errors and inconsistencies in the data. Adverse events and concomitant medications terms will be coded using the Medical Dictionary for Regulatory Authorities (MedDRA) and a custom drug dictionary. Electronic case report forms (including queries and audit trails) will be retained by Novartis, and copies will be sent to the investigator to maintain as the investigator copy.

In all cases, subject initials will not be collected or transmitted to Novartis according to Novartis policy.

## **10. DATA ANALYSIS AND STATISTICAL CONSIDERATIONS**

### **10.1. Hypotheses**

No statistical hypotheses are being tested. Only descriptive methods will be used to summarize of the data obtained from this study.

### **10.2. Study Design Considerations**

#### **10.2.1. Sample Size Considerations**

The sample size will be based on the number of subjects completing their parent study of eltrombopag who are eligible for inclusion in this rollover study.

#### **10.2.2. Sample Size Re-estimation**

Sample size re-estimation is not planned for this study.

### **10.3. Data Analysis Considerations**

#### **10.3.1. Analysis Populations**

The All Treated Subjects (ATS) Population will consist of all subjects that receive at least one dose of eltrombopag on this study. All data will be evaluated based on this population.

#### **10.3.2. Analysis Data Sets**

Construction of data sets relating to the reporting and analysis of study data will be performed in accordance with applicable Novartis standards and procedures.

### **10.3.3. Interim Analysis**

Data will be summarized whenever a sufficient number of subjects in each cohort has accrued to warrant the evaluation of safety data. This will be determined by the study team and may occur multiple times. No decisions will be made at the time of interim analyses to alter the study in any way. All available data at the time of an interim analysis will be included.

### **10.3.4. Key Elements of Analysis Plan**

Data will be listed and summarized according to the Novartis reporting standards, where applicable. Complete details will be documented in the Reporting and Analysis Plan (RAP). Any deviations from, or additions to, the original analysis plan described in this protocol will be documented in the RAP and final study report.

As it is anticipated that accrual will be spread thinly across centers and summaries of data by center would be unlikely to be informative, data from all participating centers will be pooled prior to analysis.

All data up to the time of study completion/withdrawal from study will be included in the analysis, regardless of duration of treatment.

As the duration of treatment for a given subject will depend on efficacy and tolerability, the duration of follow-up will vary between subjects. Consequently there will be no imputation for missing data.

As this is an open label, single arm study, no statistical comparisons will be made. Data will be summarized where appropriate.

Demographic and baseline characteristics will be summarized.

#### **10.3.4.1. Safety Analyses**

Safety assessments are described in Section 3 and Section 8.4.

The ATS population will be used for the analysis of safety data. Complete details of the safety analyses will be provided in the RAP.

The number of subjects administered study medication will be summarized according to the duration of therapy.

##### **10.3.4.1.1. Adverse Events**

Adverse events (AEs) will be coded using the standard MedDRA and grouped by system organ class. AEs will be graded by the investigator according to the National Institutes of Health (NCI)-CTCAE (version 4.0).

Events will be summarized by frequency and proportion of total subjects, by system organ class and preferred term. Separate summaries will be given for all AEs, drug-related AEs, serious AEs and AEs leading to discontinuation of study medication.

If the AE is listed in the NCI CTCAE (version 4.0) table, the maximum grade will be summarized.

Characteristics (e.g. number of occurrences, action taken, grade, etc) of the following AEs of special interest may be summarized separately: hepatotoxicity and thromboembolism.

The incidence of deaths and the primary cause of death will be summarized.

#### **10.3.4.1.2. Clinical Laboratory Evaluations**

Hematology and clinical chemistry data will be summarized at each scheduled assessment according to NCI CTCAE grade (version 4.0). The proportion of values lying outside the reference range will also be presented for laboratory tests that are not graded because there are no associated NCI CTCAE criteria. Summaries will include data from scheduled assessments only, and all data will be reported according to the nominal visit date for which it was recorded (i.e. no visit windows will be applied). Unscheduled data will be included in “overall” and “any post-screening” summaries which will capture a worst case across all scheduled and unscheduled visits post first dose of study medication. Further details will be provided in the RAP.

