### **1.3.5. Risk Management**

Risk management strategies for eltrombopag are in place for patient safety.

Novartis has a robust risk management plan (RMP) for eltrombopag where the presentation and management of risks are conveyed. Safety data continue to be collected and analyzed for eltrombopag since the initial approval of PROMACTA™ (eltrombopag) in the United States in 2008 and the subsequent approval of REVOLADE™ (eltrombopag) in the EU in 2010.

A comprehensive Risk Management Plan (RMP) is in place for eltrombopag. Identified risks described in the RMP include hepatobiliary laboratory abnormalities, thromboembolic events, post therapy reoccurrence of thrombocytopenia, and hepatic decompensation in patients with hepatitis C. Potential risks in the RMP include increased bone marrow reticulin formation, cataract, renal tubular toxicity, and photosensitivity.

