**Table 5 Laboratory Assessments**

Hematology	Standard Chemistry
Hemoglobin	Blood urea nitrogen or urea
Hematocrit	Creatinine
Red blood cell count	AST
Platelets	ALT
White blood cell count with differential	Total bilirubin
Total neutrophils	Direct bilirubin
Lymphocytes	Albumin
Monocytes	Pregnancy
Eosinophils	Serum $\beta$ -hCG (human chorionic gonadotrophin)
Basophils	
Blast % from peripheral blood smear 	

1. Subjects from Cohort A only

2. Before the first dose of study treatment (-14 days) and at the investigator discretion

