### 13. APPENDICES

#### 13.1. Appendix 1 Time and Events Table

[figure not shown]
Procedures	Transition Visit 	Treatment	End of Therapy	Follow-up
		Weekly/Bi-weekly/Monthly/Bi-Monthly	End of Treatment or Early Withdrawal	30 Days after last study treatment
		Visit Window Per Figure 1 of the Protocol	(+7 days)	(+7 days)
Informed Consent 	X			
Inclusion/Exclusion criteria	X			
Demographic and Parent Study Data	X			
Physical Examination 	X	X	X	X
12-lead ECG	X			
Concomitant Medication	X	X	X	
Adverse Events	X	X	X	X
Serious Adverse Events	X	X	X	X
Hematology	X	X	X	X
Clinical Chemistry 	X	X	X	X
Pregnancy test (serum) 	X	o	o	o
Bone Marrow Examination 	o	o	o	o
Blood and Blood Supportive Care Products	X	X	X	X
Disease Response/Progression 	o	o	o	o
Dispense Study Treatment	X	X		
Assess Study Treatment Compliance		X	X	

o is used to indicate a study procedure is not required at the visit; however, it should be documented in the individual eCRF if it has been performed.

1. All subjects transitioning from parent study will begin this rollover study based on the last day of the study treatment completed during the parent study. All Transition Visit assessments/procedures must be completed prior to the first dose of study treatment in this study. The Transition Visit must occur within 28 days of the end of the last day of the study treatment and may be on the same day as the last study treatment visit of the parent study. Assessments/procedures may be used to fulfill the requirements of both the parent study and this study.
2. Informed consent must be obtained prior to performing any assessments or procedures for this study and before treatment with eltrombopag in this study.
3. PI must document that subject is acceptable to continue study treatment in the subject's source documents.
4. Refer to Table 5 for complete list of clinical laboratory assessments to be performed.
5. To be performed prior to first study treatment and at the investigators discretion. Pregnancy test only performed in women of child-bearing potential (Section 8.4.8.1). Subjects with documentation in source records of post-menopausal status do not need to have any pregnancy tests performed.
6. To be done as per local SOC and at disease progression in Cohort A. Data to be entered into eCRF when procedures are performed.
7. Collected in Cohort A subjects only when assessed as per SOC.

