## 2.7.3 Laboratory data

Laboratory values will be converted to the international system of units (SI). CTCAE Grade 0 will be assigned for all non-missing values not graded as 1 or higher. Grade 5 will not be used. For laboratory tests where grades are not defined by CTCAE version 4.03, results will be categorized as low/normal/high based on laboratory normal ranges.

The following summaries will be provided. Note that except for baseline value only on-treatment values will be used in summaries.

- Shift tables using CTCAE grades to compare baseline to the worst on-treatment value for platelets, hemoglobin and white blood cells (WBCs).
- Summary table for platelet counts over time.

Listings of all available laboratory data (hematology, biochemistry, urinalysis, coagulation, pregnancy test etc.) will be provided showing the corresponding CTCAE grades, if applicable, and the classifications relative to the laboratory normal ranges. Values measured outside of on-treatment period will be flagged.

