## **4 Change to protocol specified analyses**

For laboratory results, grades will be defined by CTCAE version 4.03 and not version 4.0. Vital signs and ECG data will only be listed. Existing Pharmacokinetic samples were not analysed due to instability issues, any future samples, if analysed, will be listed.

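### SAP 2.7.3 tabulates 6 of the 18 scheduled laboratory tests, leaves creatinine and neutrophils to listings, and does not declare this departure from protocol 10.3.4.1.2

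*Protocol*

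**What the plan says.** **Protocol.** Section 10.3.4.1.2 makes three commitments on laboratory data and excepts no test.

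- By-visit grading: "Hematology and clinical chemistry data will be summarized at each scheduled assessment according to NCI CTCAE grade (version 4.0").
- Ungraded tests: "The proportion of values lying outside the reference range will also be presented for laboratory tests that are not graded".
- Worst case: unscheduled results enter overall summaries, "which will capture a worst case across all scheduled and unscheduled visits post first dose of study medication".

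Table 5 is the scheduled panel. The Time and Events Table (Appendix 1) has hematology and chemistry at every visit from transition to follow-up and says "Refer to Table 5 for complete list of clinical laboratory assessments to be performed". Section 10.3.4 requires departures from the protocol's analysis plan to be recorded in the RAP and the final report.

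**SAP.** Section 2.7.3 plans these summaries:

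- "Shift tables using CTCAE grades to compare baseline to the worst on-treatment value for platelets, hemoglobin and white blood cells (WBCs");
- one table of platelet counts over time;
- the number (%) of patients by worst on-treatment value for total bilirubin, ALT, AST and ALP, against multiples of the upper limit of normal.

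All other laboratory results are listed, with a CTCAE grade where applicable and a normal-range class. Section 4 (changes to protocol-specified analyses) has one laboratory entry: "For laboratory results, grades will be defined by CTCAE version 4.03 and not version 4.0". It also declares that vital signs and ECG are only listed, and it explains the handling of pharmacokinetic samples.

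**The concern.** Safety is the only objective that the SAP analyses (Sections 2.5 and 2.6). A laboratory test that moves from a promised table to a listing loses its count of affected subjects and its comparison with baseline, and the report's reader has to build both.

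Two omissions stand out. The first is creatinine, because protocol 1.3.5 names a renal risk: "Potential risks in the RMP include increased bone marrow reticulin formation, cataract, renal tubular toxicity, and photosensitivity". The second is neutrophils, because adverse event reporting in Cohort A (MDS/AML) has disease-related exemptions that could keep a fall in neutrophils out of the AE tables as well.

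The change is also undeclared. Section 4 shows that the SAP's authors do record a move to listing-only when they recognise one, as they did for vital signs and ECG. A reader of Section 4 would conclude that laboratory reporting otherwise follows the protocol.

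**Working it through.** The plan states no figure to reproduce, so the check is a count of Table 5 rows against the SAP's tables.

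**Scheduled tests (protocol Table 5)**

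- Hematology, 11 rows: hemoglobin, hematocrit, red cells, platelets, white cells, neutrophils, lymphocytes, monocytes, eosinophils, basophils, blast %.
- Chemistry, 7 rows: urea, creatinine, AST, ALT, total bilirubin, direct bilirubin, albumin.
- Total: 11 + 7 = 18, not counting the pregnancy test.

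**Tabulated in SAP 2.7.3**

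- Shift tables: platelets, hemoglobin, white cells = 3.
- Liver table: total bilirubin, ALT, AST = 3. ALP is also in this table but is not a Table 5 test.
- Total from Table 5: 3 + 3 = 6.

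**Result**

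| Type of summary | Table 5 tests covered |
|---|---|
| Any summary table | 6/18 = 33% |
| Summary by CTCAE grade | 3/18 = 17% |
| Summary over time | 1/18 (platelets; no grading stated) |
| Chemistry by CTCAE grade | 0/7 |
| Listing only | 18 − 6 = 12 |

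The 12 listing-only rows are hematocrit, red cells, neutrophils, lymphocytes, monocytes, eosinophils, basophils, blast %, urea, creatinine, direct bilirubin and albumin.

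**Sensitivity to how rows are counted**

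- Without blast % (Cohort A only): 6/17 = 35%.
- With the pregnancy test: 6/19 = 32%.
- White cells and their five differential rows as one test: 18 − 5 = 13, so 6/13 = 46%.

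Creatinine and neutrophils have no table of their own under any of these.

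**The three commitments against the SAP**

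1. Graded summaries at each scheduled assessment: none planned. Platelets over time is the nearest.
2. Out-of-range proportions for ungraded tests: none planned. The SAP assigns low/normal/high classes, but 2.7.3 tabulates them for no test.
3. Worst-case summaries: met in part. The shift and liver tables use the worst on-treatment value and are not restricted to scheduled visits, but they cover only the six tests above.

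**Is it declared anywhere?** Section 4 is silent. The SAP document history has a generic entry on removed analyses that lists 2.7.3. It names no test and compares with the previous SAP, not with the protocol. The small-sample reason given there applies only to showing platelet counts by table.

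**The case against.** The strongest reply is that little safety information is lost in a hypothesis-free access study with 22 subjects. Much of that stands.

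- **AE tables catch a good deal.** Protocol 8.4.4.3 requires an adverse event for any laboratory result that leads to an intervention, including a dose change, and for abnormalities judged clinically significant. SAP 2.7.1 counts subjects with such events. A reader might infer that renal change, neutropenia or high platelets would appear in no count at all; the documents do not support that. The limit is that 8.4.4.3 exempts findings associated with the underlying disease unless worse than expected, and 8.4.4.6.1 treats infections in the natural course of MDS/AML as non-reportable. Some Cohort A cytopenias could therefore escape both sets of tables.
- **Creatinine is still reported.** It is missing from the tables, not from the listings, and a listing of 22 subjects can be tallied by hand. The renal risk is a potential one. The AESI tables draw on a retrieval strategy that is not in the documents, so whether they count renal events is unknown.
- **Twelve of 18 overstates the information lost.** Hematocrit and red cells overlap with hemoglobin, direct with total bilirubin, and the differential with white cells. The count measures the departure, not the lost safety content.
- **High platelets remain visible.** A shift table with one worst value per subject might seem to hide them. However, the platelet table over time would carry a minimum and maximum under SAP 2.1, and counts that trigger a dose change fall under 8.4.4.3. Counts of subjects above 200 or 400 Gi/L were never promised, so their absence is not a departure.
- **The protocol leaves details to the RAP.** That allows further specification. It does not waive the duty in 10.3.4 to document deviations.

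**Conclusion.** The departure is real and undeclared. Of 18 scheduled tests, 6 are tabulated, 3 of them by CTCAE grade and 1 over time, and no out-of-range proportions are planned. Creatinine and neutrophils are the omissions that matter most.

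The consequence is modest. The loss is partial because of the AE rules and the listings. It is greatest for abnormalities that are not acted on or are attributed to underlying disease. Small numbers also limit what the missing tables could show: if none of 22 subjects had a given abnormality, the one-sided 95% upper limit would still be 1 − 0.05^(1/22) = 12.7%, and wider within a cohort. This supports a correction worth making. It does not support a claim that the safety analysis fails.

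The conclusion assumes that the SAP is the document the protocol calls the RAP, and that Section 4 is where deviations from the protocol are meant to be declared.

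**What to change.** 1. In SAP 2.7.3, extend the baseline-to-worst on-treatment shift table to creatinine and neutrophils at least, and preferably to the other Table 5 tests, using low/normal/high where CTCAE defines no grade. State that scheduled and unscheduled values both count.
2. In SAP Section 4, declare and justify every test left as listing-only, and the omission of by-visit graded summaries and out-of-range proportions. Carry the same statement into the study report.
3. Optionally, add the number (%) of subjects with any platelet count above 200 and above 400 Gi/L. This is an improvement in reporting, not a protocol commitment.

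The SAP already assigns the grades and classes, so the cost is a few more runs of an existing table program and some wording. The drawback is sparse tables: with 22 subjects in two cohorts, many cells will hold zero or one.
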